- 383 Study participants who are determined to be ineligible for any reason (including 0 384 pregnancy) prior to biopsy will not proceed to biopsy or transplant, and will either 385 discontinue or postpone and re-screen at a later time. 386 After biopsy but prior to transplant 387 Study participants who become pregnant will consult with the study doctor and their \circ 388 Obstetrician/Gynecologist or primary care physician before determining if it is safe for 389 them to continue with the transplant procedure. If the decision is made not to 390 continue with the transplant procedure, the participant will either discontinue or 391 postpone and re-screen at a later time. 392 Study participants who are determined to be ineligible for any other reason will 0 393 consult with the study doctor before determining if it is safe for them to continue with 394 the transplant procedure. If the decision is made not to continue with the transplant 395 procedure, the participant will either discontinue or postpone and re-screen at a later 396 time. 397 Study participants for whom the biopsy fails to generate a viable cell sheet may be 0 398 evaluated for a second biopsy according to Section 5.6 above. If the participant does 399 not proceed to second biopsy for any reason, or a second biopsy also fails to 400 generate a viable cell sheet, the participant will discontinue. 401 Additionally: Regardless of whether a participant will discontinue, all participants 0 402 who had a biopsy and do not proceed to transplant will be monitored by the study team for 30 days to check for any adverse events related to the biopsy procedures. 403 404 If the donor eye after biopsy has a complication or adverse event that does not 405 resolve after 30 days, the study team will also monitor the donor eye until the 406 complication resolves. Those meeting criteria to discontinue, as detailed in the 407 scenarios above, will discontinue after this time. 408 After transplant 409 In general, all possible efforts will be employed to ensure participants who completed 0
- 410
- In general, all possible efforts will be employed to ensure participants who completed transplant are retained through the duration of follow up.

411412 **5.8. TERMINATION OF STUDY**

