959 Participants will be asked to report any pregnancies that occur within three days prior to 960 surgery. 961

962 6.8.8. CORNEAL RECONSTRUCTION WITH CALEC (DAY 0)

963 Participants will undergo corneal reconstruction within 24 hours of release of CALEC.

964	
965	A detailed description of the procedures can be found in Section 6.2.2. All participants will be
966	discharged the day of surgery, unless unforeseen complications prohibit discharge. If a
967	participant is admitted for observation, the Day 1 post-operative visit will occur while the
968	participant is in the hospital. All other visits will follow as originally scheduled.
969	
970	6.8.9. FOLLOW-UP PERIOD
971	Each participant will be followed for a period of 18 months from the time of the transplantation.
972	
973	Participants will be asked to report any pregnancies that occur within seven days after
974	transplant.
975	
976	6.8.10. POST-TRANSPLANT (DAY 1)
977	Slit lamp examination (both eyes) including
978	 Corneal opacification (as defined by Fantes Scale) (both eyes)
979	• Staining with fluorescein (extent of staining and epithelial defect area) (donor eye
980	required; recipient eye at discretion of investigator)
981	 Visual acuity (BCVA)(both eyes)
982	Intraocular pressure (both eyes)
983	Slit lamp photographs (both eyes) by certified technician, including
984	 Photography for neovascular area
985	• Photography (with fluorescein) for epithelial defect (donor eye required; recipient
986	eye at discretion of clinician)
987	 Punctal plugs, if needed (Section 6.5.5) (both eyes)
988	 Application of bandage contact lens, if needed (Section 6.5.5)
989	Adverse event assessment
990	
991	6.8.11. POST-OP FOLLOW-UP: WEEKS 1, 2, MONTH 1 (4 WEEKS ± 3 DAYS) AND
992	MONTHS 3, 6, 9, 12 (13, 26, 39, 52 WEEKS ± 1 WEEK), AND MONTHS 15, AND 18 (65 AND
993	78 WEEKS ±2 WEEKS)
994	 Symptom assessment (every visit except week 1, week 2, month 1)
995	 Slit lamp examination (both eyes) including
996	 Corneal opacification (as defined by Fantes Scale) (both eyes)
997	 Staining with fluorescein (extent of staining and epithelial defect area) (donor eye
998	required; recipient eye at discretion of investigator at week 1 and 2, and required at
999	month 1 and thereafter.)
1000	 Visual acuity BCVA (both eyes)
1001	Intraocular pressure (both eyes)
1002	 Slit lamp photographs (both eyes) by certified technician, including
1003	 Photography for neovascular area

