Vancomycin ²		Х				Х	x	fter	ö	х	Х	X	х	X ¹	X ¹	X ¹	X ¹	X ¹	X ¹
Artificial Tears								bio		X	х	X	x	х	х	х	x	х	Х
20% Autologous Serum Drops								psy		X	X	X	X ¹	X ¹	X ¹	X ¹	X ¹	X ¹	X ¹
Symptom Assessment		X												х	x	X	X	х	X
Adverse Event Assessment		X (changes in medical status)				x	x			x	х	х	x	x	x	x	x	x	x

Cell Transplantation in the Treatment of Limbal Stem Cell Deficiency

1486 1487

1489

1504

1505 1506

1507 1508

1510

1511

1512

1513

1515

1516

1517

1488 15. PROTOCOL ADDENDUM: SECOND TRANSPLANT

1490 **15.1. OVERVIEW**

Some study participants who received CALEC and for whom epithelial defect and conjunctivalization has not resolved after 12 months may benefit from an additional transplant. Participants meeting study criteria (section 15.3) may be offered the opportunity to undergo a second procedure, either CALEC or CLAU. The following chapter outlines the protocol that will be followed for these participants. Up to three participants can receive a second transplant.

1497 **15.2. CRITERIA FOR SECOND TRANSPLANT**

- All of the following criteria must be met in order for a participant to be considered for a second transplant.
- Participant previously received CALEC (participants previously receiving CLAU will not be eligible)
- Second transplant cannot occur prior to the 12-month visit
- Presence of epithelial defect in recipient eye
 - Must have been present at 2 or more visits (>1 month between visits), any time on or after the 3-month visit
 - >1 mm in any dimension
 - (Note: Does not need to be present at the Screening/Baseline visit prior to second transplant)
- Presence of conjunctivalization / fibrovascular pannus in recipient eye
 - Must be present at the Screening/Baseline visit prior to second transplant
 - >2 mm from the limbus
 - ≥6 clock hours
 - Investigator discretion that repeat transplant has therapeutic potential
- Absence of the following in the donor eye:
 - Conjunctivalization of the cornea defined by fibrovascular pannus more than 2mm from the limbus into the cornea for ≥3 clock hours
 - Lack of limbal palisades of Vogt for ≥3 clock hours
 - History of allo-limbal transplantation
- 1518 1519

1522

1527

1532 1533

1534

1535

1520 NOTE: these criteria are independent of whether the participant meets the protocol definition of 1521 complete or partial success.

1523 15.3. INFORMED CONSENT PROCESS

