Safety and Feasibility of Cultivated Autologous Limbal Epithelial PI: [name] Cell Transplantation in the Treatment of Limbal Stem Cell Deficiency 1536 • Hematologic lab screening will include only the blood draw collected within 1-7 days as required for manufacturing of the graft per DCDI protocol 1537 Hepatitis B 1538 Hepatitis C 1539 1540 HIV 1541 Slit lamp exam 0 1542 o BCVA o IOP 1543 1544 Fundus exam or B-scan 0 • AS-OCT 1545 1546 o IVCM 1547 Slit lamp photos Symptom assessment 1548 Conjunctival swab and culture 1549 (if MRSA positive, the original protocol will be followed for vancomycin) 1550 Schirmer's test (optional) 1551 0 Punctal plus (optional) 1552 0 The visit will not require punctal plugs, bandage contact lenses, prednisolone, vancomycin, 1553 preservative-free tears and autologous 1554 serum tears as participants will already be using them as treatments from initial CALEC. The 1555 preoperative antibiotic drop will be given prior to the biopsy and transplant in the respective operative 1556 eyes, as with the initial CALEC (section 6.2.1). The Schirmer test may not be needed as participants 1557 would have had it to receive the initial CALEC and would have had plugs if necessary. . The full set of 1558 1559 labs will not be repeated as they would have been done to enter the study for the initial CALEC. The labs that are required for manufacturing of CALEC will be repeated as noted above, for participants 1560 1561 pursuing second CALEC transplant. 1562 **15.5. BIOPSY AND TRANSPLANT** 1563 1564 1565 For participants choosing to undergo CLAU The pre-operative visit will occur within 60 days after baseline and within 1-5 days prior to 1566 transplant, and testing will include slit lamp exam, visual acuity, IOP. 1567 The biopsy and transplant procedures and subsequent medication regimens will follow standard 1568 1569 care. 1570 1571 For participants choosing to undergo CALEC The post-biopsy and pre-operative visits and testing schedule, including all procedures and 1572 measurements, will be the same as the current protocol (APPENDIX VI). 1573 The CALEC manufacturing (section 6.1), biopsy and transplant procedures (section 6.2) and 1574 subsequent medication regimens (section 6.5) will follow the protocol for initial CALEC 1575 If a participant experiences failure of the biopsy to generate a viable cell sheet, the participant 1576 will not be eligible to rescreen for another biopsy attempt. The participant will be monitored by 1577 the study team for 30 days to check for any adverse events related to the biopsy procedures. If 1578 the donor eye has a complication or adverse event that does not resolve after 30 days, the study 1579 team will continue to monitor until it resolves. The participant will discontinue the study after the 1580 monitoring period. 1581

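### After a failed second-CALEC biopsy, Section 15.5 ends study follow-up while the first graft is still in its 18-month observation, and Section 15.7 does not say whether primary data stop at that biopsy

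*Protocol*

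**What the plan says.** The addendum in Protocol Section 15 offers a second procedure, CALEC or CLAU, to participants who already received CALEC. Section 15.1 sets a limit: "Up to three participants can receive a second transplant". Under Section 15.2 the second transplant may not precede the 12-month visit, and no latest date is given. The recipient eye must have shown an epithelial defect at two or more visits and must have pannus over at least 6 clock hours.

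Under Section 15.5, a participant whose second-CALEC biopsy fails "will not be eligible to rescreen for another biopsy attempt". Monitoring follows by "the study team for 30 days to check for any adverse events related to the biopsy procedures", and longer if a donor-eye event persists. Then: "The participant will discontinue the study after the" monitoring period. No exception is made for unfinished follow-up of the first graft.

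Other sections point the other way:
- Section 3 plans 18 months of follow-up for all participants who complete a transplant.
- Section 5.7, After transplant: "In general, all possible efforts will be employed to ensure participants who completed transplant are retained through the duration of follow up".
- Section 6.8.9: "Each participant will be followed for a period of 18 months from the time of the transplantation".
- Section 15.6 keeps participants who opt for a second transplant on the visit schedule until a common closeout date.

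Sections 15.7.1 and 15.7.3 restrict the primary safety and efficacy analyses to data before the date of the biopsy for the second transplant. The SAP does not mention second transplants.

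**The concern.** Section 15.5 appears to carry over the Section 5.7 rule for people who never had a graft. There, if a second biopsy also fails to "generate a viable cell sheet, the participant will discontinue". That is reasonable when there is no graft to follow. In the addendum everyone has one, and a failed biopsy changes nothing in the recipient eye.

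The result is uneven. A participant who declines a second transplant stays to month 18, and one who receives it is followed to closeout. Only the one whose biopsy failed is sent out, and no reason is given.

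Primary quantities are touched. The primary safety objective is incidence through 18 months, and SAP Section 5.0 reports it as simple percentages of transplanted participants. An early exit can therefore remain in the denominator with later events unseen, which pulls the estimate down. Month 18 is also a primary efficacy time point. SAP Section 5.0 fills missing Complete Success by multiple imputation with logistic regression, but these eyes are selected on poor first-graft status, so missing at random is doubtful. The value cannot simply be set to failure either, because Section 15.2 says its criteria are independent of the success definitions.

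**Working it through.** **The plan's own figures.** SAP Section 4.0 uses 15 CALEC participants. With zero events the exact 95% upper limit is 1 − 0.025^(1/n). For n = 15 this is 21.8% (SAP: 22%). The chance of seeing at least one event at a 5% rate is 1 − 0.95^15 = 0.54 (SAP: 0.54). Both reproduce.

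**Earliest biopsy.** Section 15.4 says these participants will have been followed for at least a year by the combined screening/baseline visit, and the biopsy comes after that visit. Month 12 is week 52, day 52 × 7 = 364.

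**Time lost.** Month 18 is week 78, day 546.
- Biopsy on day 364, exit on day 364 + 30 = 394.
- Observation lost: 546 − 394 = 152 days, about 5 months.

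**Visits lost.** A visit is missed if biopsy day + 30 falls before its window opens (windows from Section 6.8.11).
- Month 15 (65 ± 2 weeks) opens on day 63 × 7 = 441, so it is missed if the biopsy is on or before day 410 (about month 13.5).
- Month 18 (78 ± 2 weeks) opens on day 76 × 7 = 532, so it is missed if the biopsy is on or before day 501 (about month 16.5).
- From day 502 the monitoring reaches the month-18 window and no visit need be lost.

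**The analysis cut.** If the Section 15.7 cut covers a failed biopsy, primary data stop at the biopsy. For day 364 that removes 546 − 364 = 182 days, including the 30 monitored days. The month-18 result would then leave the primary analysis for any biopsy before that visit, even one after day 501. Keeping the participant in the study would not by itself restore it.

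**How many.** The documents give neither the number of second-CALEC biopsies nor a failure rate for them. I assume up to three biopsies and apply the 5-10% construct failure rate in SAP Section 3.0 to each. P(at least one failure) = 1 − (1 − p)^k:

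| Biopsies k | p = 5% | p = 10% |
|---|---|---|
| 1 | 5% | 10% |
| 2 | 10% | 19% |
| 3 | 14% | 27% |

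The expected number for k = 3 is 0.15 to 0.30. As a stress case, p = 50% (the halting guideline's four failures in eight) gives 1 − 0.5^3 = 88% and 1.5 expected.

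**Weight of each case.** Section 5.5 caps enrollment at 17 transplants. One missing eye adds 1/17 = 5.9 points of worst-to-best-case range to the month-18 success rate. If that eye also drops out of the safety denominator, the zero-event upper limit moves from 19.5% (n = 17) to 20.6% (n = 16).

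**The case against.** The case for leaving the text alone has real content. Efficacy is exploratory and primary safety is descriptive. The addendum is a specific rule for a special group, and the retention rule in Section 5.7 is qualified as a general one. Month-3 and month-12 data will normally be in hand, and the month-15 visit is optional where travel is prohibitive. Section 6.8.12 offers an early termination visit with symptoms, slit lamp examination, staining, photographs and adverse events. Section 15.6 can be read to cover someone who chose a second CALEC but never received it, which would keep that person to closeout.

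These points reduce the size of the problem but do not remove it. An exit visit near month 13 is not a month-18 observation. The reading of Section 15.6 adds a further conflict with Section 15.5 instead of settling it. Sections 3 and 6.8.9 carry no qualifier.

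A reader might infer four stronger things that the documents do not support:
- That month 18 is always lost. It is lost to observation only for biopsies up to about day 501.
- That the biopsy could fall near month 11, by counting back 10 to 30 days of manufacturing from the 12-month limit, so that six months of observation are lost. Sections 15.1 and 15.4 place the process after a year of follow-up.
- That more than three participants will be affected, since the cap counts transplants received and not biopsies attempted. The wording does not exclude this, but nothing in the documents makes it likely. CLAU is an alternative, and a biopsy succeeds if any one construct passes.
- That discontinuation alone costs the primary data. Section 15.7 may do so on its own.

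**Conclusion.** The contradiction holds. Section 15.5 ends follow-up of a first graft that Sections 3, 5.7 and 6.8.9 want observed for 18 months, and Section 15.7 leaves open whether a biopsy without a transplant triggers the primary data cut.

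The effect is conditional and small in number: at most about 152 days of lost observation per participant, and probably 0 or 1 participants. Each weighs 5.9 points at month 18, and the loss falls on eyes in poor condition. This rests on an earliest biopsy near month 12, exit at the 30-day minimum, three second-CALEC biopsies, and a construct-level failure rate used per biopsy. Severity is moderate or lower. It merits correction because the loss would be caused by the protocol itself and missed visits cannot be recovered.

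**What to change.** Reconcile Sections 15.5, 15.6, 15.7, 5.7 and 6.8.9 together.

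- **Section 15.5:** replace the discontinuation sentence. After donor-eye monitoring, the participant stays on the visit schedule timed from the first transplant through month 18, or leaves once monitoring ends if month 18 has passed.
- **Section 15.6:** say whether its schedule applies to participants who chose a second transplant or only to those who received one.
- **Sections 15.7.1 and 15.7.3:** state that when no second transplant was performed, the cut does not apply to recipient-eye primary safety events or efficacy data. Donor-eye and other events related to the second biopsy stay in the separate summary, so that harvest complications are not counted against the first graft.
- **SAP Section 5.0:** add these rules, and say how month-18 Complete Success is handled if it is still missing for such a participant.

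The cost is one sentence in 15.5, a clarification in 15.6, one clause in 15.7 and a short SAP entry. Each affected participant attends at most two visits that were already scheduled. No new procedure is needed, and the change concerns follow-up and analysis only.

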
Cell Transplantation in the Treatment of Limbal Stem Cell Deficiency

1582										
1583										
1584	15.6. STUDY PROCEDURES, MEASUREMENTS, AND VISIT SCHEDULE									
1585										
1586	For all participants choosing to undergo a second transplant (either CALEC or CLAU), the post-									
1587	operative visit and testing schedule, including all procedures, measurements and data collection, will be									
1588	the same as the current protocol (APPENDIX VI). The protocol schedule will be followed until a									
1589	common study closeout date is reached.									
1590										
1591	15.7. ANALTSIS CONSIDERATIONS 15.7.1 SΔFFTY									
1592	 Safety events of interest as defined in section 7.1.1. 									
1593	• Primary safety analysis for protocol objective: Safety events will only be tabulated up									
1595	to (not including) the date of the biopsy for the second CALEC or CLAU transplant									
1596	 Additional analysis evaluating second CALEC transplant: Safety events following the 									
1507	bionsy for the second CALEC transplant will be summarized separately									
1397	biopsy for the second CALLO transplant will be summarized separately.									
1598										
1599	15.7.2. FEASIBILITY									
1600	 Feasibility measures, as defined in section 7.1.2.: 									
1601	 Primary feasibility analysis for protocol objective: The biopsy attempts for only the 									
1602	initial CALEC transplants will be included in the primary feasibility outcome calculation of									
1603	feasibility success									
1604	 Additional analysis evaluating second CALEC transplant: The biopsy attempts for 									
1605	second CALEC transplant will be summarized separately									
1(0)										
1606										
1608	 Efficacy outcome measures as defined in section 7.2 will be evaluated the following 									
1609	ways:									
1610	 Primary efficacy analysis for protocol objective. Efficacy outcome data will only be 									
1611	included up to (not including) the date of biopsy for the second CALEC or CLAU									
1612	transplant									
1612	 Additional analyses evaluating second CALEC transplant. 									
1614	 Efficacy outcome data will be evaluated relative to original baseline through the 									
1615	latest protocol visit prior to the study closeout date									
1616	 Efficacy outcome data will be evaluated relative to second CALEC baseline 									

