5.0 Statistical Analysis Plan

Safety Analysis

 Coding of all adverse events for analysis will be based on the MedDRA coding determined by the Medical Monitor. The following safety analyses will be performed.

1. Primary Safety Analysis (within-CALEC group evaluation of primary safety outcomes):

- a. The primary safety events of interest (ocular infection, corneal perforation, and graft detachment >=50%) in the recipient eye will be summarized as the numbers and percentages (and 95% exact confidence intervals) of participants having each event and the number and percentage (and 95% exact confidence intervals) of participants having any of the three events, up to 18 months.
 - These events will be evaluated in CALEC Group Phase A and Phase B participants combined. Only participants who completed transplant and only events occurring after transplant will be included.

2. Primary Safety Analysis (CALEC versus CLAU comparison of primary safety outcomes):

- a. The primary safety events of interest (ocular infection, corneal perforation, and graft detachment >=50%) in the recipient eye will be summarized as the numbers and percentages (and 95% exact confidence intervals) of participants having each event and the number and percentage (and 95% exact confidence intervals) or participants having any of the three events, up to 18 months
 - i. These events will be evaluated within each treatment group, in Phase B participants only. All participants who were randomized will be included regardless of whether transplant was completed. Phase B participants who discontinued prior to randomization will not be included. All events occurring after randomization will be included. Events prior to randomization will not be included.
- b. The two treatment groups will also be compared by computing the differences in percentages (and 95% exact confidence intervals) having each event and the difference in percentages (and 95% exact confidence intervals) having any of the three events.
- 3. Secondary Safety Analysis (explore/evaluate all adverse events): All reported adverse events up to 18 months (including systemic, recipient, and donor eye events) will be evaluated as follows.

- a. Within each MedDRA system organ class, tabulate the number and percentage of participants having at least 1 event within the given system organ class. Evaluate both of the following ways:

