 - i. Within-CALEC group: Evaluate in CALEC Group Phase A and Phase B participants combined. Only participants who completed transplant will be included. Only events occurring after transplant will be included.
 - ii. CALEC versus CLAU comparison: Evaluate within each treatment group, in Phase B participants only. All randomized participants will be included regardless of whether transplant was completed. Phase B participants who discontinued prior to randomization will not be included. All events occurring after randomization will be included. Events prior to randomization will not be included.
- b. Within each adverse event term (MedDRA lower level term), tabulate the number of events and number of participants with at least 1 event, separately for systemic, recipient eye, and donor eye events. Evaluate the data in both of the following ways:
 - Within-CALEC group: Evaluate in CALEC Group Phase A and Phase B participants combined. Only include participants who completed transplant and only include events occurring after transplant.
 - ii. CALEC versus CLAU comparison: Evaluate within each treatment group, in Phase B participants only. All participants who were randomized will be included regardless of whether transplant was completed. Phase B participants who discontinued prior to randomization will not be included. All events occurring after randomization will be included. Events prior to randomization will not be included.
- 4. Additional Safety Analyses for DSMC Monitoring Purposes Only:
 - a. The mean number of events per patient will be calculated as the total number of events reported in the treatment group, divided by the total number of patients in the treatment group. Evaluate the data in both of the following ways:
 - i. Within-CALEC group: Evaluate in CALEC Group Phase A and Phase B participants combined. Include only participants who completed transplant and include only events occurring after transplant.
 - ii. *CALEC versus CLAU comparison*: Evaluate within each treatment group in Phase B participants only. All participants who were randomized will be included regardless of whether transplant was completed. Phase B participants who discontinued prior to randomization will not be included. All events occurring after randomization will be included. Events prior to randomization will not be included.

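### After a second transplant with CLAU, recipient-eye primary safety events have no planned separate summary, and the SAP's secondary within-CALEC adverse-event tables have no cut-off at the second procedure

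*Protocol*

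**What the plan says.** **Second procedure.** Protocol section 15.1 allows a "second procedure, either CALEC or CLAU". It also sets the number: "Up to three participants can receive a second transplant". Section 15.2 sets the earliest time: "Second transplant cannot occur prior to the 12-month visit". No latest time is given. Section 15.6 keeps the same post-operative visits and data collection for both re-graft types until a common closeout date.

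**Protocol safety analysis.** Section 15.7.1 opens with "Safety events of interest as defined in section 7.1.1". In section 7.1.1 the primary events are ocular infection, corneal perforation and graft detachment of at least 50%, all in the recipient eye. Section 15.7.1 then tabulates events for the primary safety analysis only up "to (not including) the date of the biopsy for the second CALEC or CLAU transplant". One further analysis follows, and it begins "Additional analysis evaluating second CALEC transplant: Safety events following the" biopsy for the second CALEC. Nothing equivalent is written for a second CLAU.

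**SAP safety analysis.** Item 3 of the Safety Analysis in SAP section 5.0 is wider: "All reported adverse events up to 18 months (including systemic, recipient, and donor eye events) will be evaluated as follows". For the within-CALEC version of the table by adverse event term, the rule is "Only include participants who completed transplant and only include events occurring after transplant". The system-organ-class table has the same rule. Neither mentions a second procedure. The SAP's CLAU column is limited to participants randomised in Phase B.

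**The concern.** The cut-off in section 15.7.1 shows that the sponsor does not want events after a second procedure mixed with those of the initial CALEC. The principle is carried through for the primary events and for a second CALEC, but not for a second CLAU, and it never reaches the SAP's secondary tables.

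The secondary tables matter here because they are where donor-eye events are shown. Protocol section 1 presents a lower risk of donor-eye limbal stem cell deficiency as an advantage of CALEC. It also says that CLAU traditionally removes two large pieces of limbus and can induce that deficiency in the donor eye. A second CLAU would take tissue from a donor eye that has already been biopsied for CALEC. If a harvest complication occurred within the SAP's 18-month window, the tables as written would show it as a CALEC donor-eye event. Section 2.3 makes the absence of major safety concerns one of the conditions for considering a larger study, so a reader of those tables needs to know which procedure came before each event.

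**Working it through.** **1. Timing.** The earliest second transplant is at the month 12 visit (52 weeks), and the SAP window ends at month 18 (78 weeks). The overlap is at most 78 − 52 = 26 weeks, about six months. It is zero if the re-graft takes place after month 18.

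**2. Where each event goes after a second CLAU, on the text as written**

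| Event after the second CLAU harvest | Primary safety analysis (Protocol 15.7.1) | Follow-on summary (Protocol 15.7.1) | SAP item 3, within-CALEC | SAP item 3, CLAU column |
|---|---|---|---|---|
| Recipient-eye primary event, before month 18 | Excluded by the cut-off | None for CLAU | Counted as CALEC | Not eligible |
| Other recipient-eye, donor-eye or systemic event, before month 18 | Not a primary event | None for CLAU | Counted as CALEC | Not eligible |
| Any event after month 18 | Excluded | None for CLAU | Outside the window | Outside the window |

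The last column follows because the participant received CALEC as a study treatment and was not randomised to CLAU.

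**3. The SAP's own precision figures.** SAP section 4.0 gives exact 95% intervals for n = 15. Recomputing the Clopper-Pearson interval gives 0/15: 0 to 21.8% (SAP 0 to 22%); 1/15: 0.2 to 31.9% (SAP 0 to 32%); 3/15: 4.3 to 48.1% (SAP 4 to 48%). These agree within rounding, and nothing here disputes them.

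**4. Size in a secondary table.** Inputs: at most 3 second transplants (Protocol 15.1) and 17 CALEC transplants if enrolment reaches its cap (Protocol 5.5). The event counts are assumed, because the documents give none. Suppose a row has no events from the initial CALEC, and k participants each have an event after a second CLAU and before month 18. The row then reads k/17:

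| k | k/17 | Exact 95% interval |
|---|---|---|
| 0 | 0% | 0 to 19.5% |
| 1 | 5.9% | 0.1 to 28.7% |
| 2 | 11.8% | 1.5 to 36.4% |
| 3 | 17.6% | 3.8 to 43.4% |

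With the cut-off applied, the row stays at 0/17 and the k events move to a separate listing. With 15 participants, one event would be 1/15 = 6.7%.

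Two features of item 3 temper this. It plans percentages by system organ class but only counts in the table split by eye, and it plans no intervals, so those above only show scale. A participant who already has an event in the same row before the second CLAU adds nothing to the participant count.

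**The case against.** The best case on the other side has five parts.

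- **Nothing goes uncollected.** Section 7.1.1 captures all adverse events in both eyes and systemically, section 7.3 promises to tabulate all reported events, and the DSMC reviews them (section 9.2). The Medical Monitor also rates each event's relationship to the cell therapy procedure. This stands. A reader might infer that harm from the CLAU harvest is lost, but the documents do not support that. What is missing is a planned summary that ties these events to the second procedure; the item 3 tables are not split by relatedness.
- **The 15.7.1 cut-off does not remove harvest harm.** Harvest harm occurs in the donor eye, and the primary events are recipient-eye only. This stands. The events cut without a replacement summary are recipient-eye events after the CLAU graft.
- **The SAP is out of date.** It still describes 2:1 randomisation to CLAU, which the protocol dropped at v5.0, and it never mentions second transplants. Counting post-CLAU events under CALEC therefore follows from silence, not from a stated rule. This stands too, but the missing second-CLAU summary is in the current protocol addendum.
- **The cut-off may be meant for all adverse events.** Section 15.7.1 refers to section 7.1.1, which covers all adverse events as well as the primary ones. On that broad reading, post-CLAU events leave the CALEC tables. They would still have no summary of their own, so a gap remains.
- **A second CLAU is outside the objectives.** The aims now concern CALEC only. That is a fair reason not to analyse CLAU efficacy. It is not a reason to leave post-CLAU events in CALEC safety tables.

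**Conclusion.** The point holds in a limited form. Recipient-eye primary events after a second CLAU have no planned separate summary. Under the SAP text as it stands, any adverse event after a second CLAU and before month 18 is counted in the within-CALEC item 3 tables, and any later event enters no SAP table.

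A reader might go further and infer that the headline CALEC safety result is contaminated, or that every CLAU complication would appear in the CALEC donor-eye table. Neither follows. SAP item 1 has no cut-off of its own, but Protocol 15.7.1 expressly sets one for the primary analysis for both re-graft types. The item 3 tables close at month 18.

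The effect is confined to descriptive secondary tables. One event is 1/17 = 5.9 percentage points if 17 are transplanted. Three of 17 (17.6%) is a ceiling: it needs all three second-transplant places to be used, all three participants to choose CLAU, all to be re-grafted before month 18, and each to have an event in the same row. It is fewer if some choose CALEC or are re-grafted later. The misattribution also rests on the narrow reading of 15.7.1; the absence of a second-CLAU summary does not. The correction should be made before the tables are produced.

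**What to change.** 1. In SAP section 5.0, Safety Analysis, item 3, state that the within-CALEC tables count events only up to, and not including, the date of the biopsy or harvest for a second transplant of either type. This is the rule that Protocol 15.7.1 already uses for the primary events.
2. In Protocol 15.7.1 and in the SAP, state that all adverse events from that date through study closeout will be listed separately by re-graft type (CALEC or CLAU) and by eye (recipient, donor, systemic), with the primary safety events identified.

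The cost is two sentences and one small table. No new data are needed, because section 15.6 already requires the same data collection after either re-graft type.
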